# 5.4.2 Justification for Investigational Product Dose for KRd and KPd Arms

The safety experience from 56 subjects with RRMM with weekly KRd 56 mg/m $^2$  (n = 10) or 70 mg/m^2 (n = 46) in Study CFZ013 (NCT02335983) has not identified any safety concerns which would preclude the investigation of KRd 56 mg/m^2 weekly in this study. The subject incidence of grade ≥ 3 treatment-emergent adverse events was 70.0% in the KRd 56 mg/m² group and 69.6% in the KRd 70 mg/m² group. Grade ≥ 3 adverse events reported in more than 2 patients were thrombocytopenia (56 mg/m $^2$ , n = 2; 70 mg/m^2, n = 4), neutropenia (56 mg/m^2, n = 1; 70 mg/m^2, n = 4), anemia (56 mg/m^2, n = 2; 70 mg/m^2, n = 3), pneumonia (70 mg/m^2, n = 4), decreased platelet count (56 mg/m^2, n = 1; 70 mg/m^2, n = 3), decreased neutrophil count (56 mg/m^2, n = 2; 70 mg/m^2, n = 2), hypertension (56 mg/m^2, n = 1; 70 mg/m^2, n = 3), and hypophosphatemia (70 mg/m^2, n = 4). There were 3 deaths in the KRd 70 mg/m^2 group (1 each due to cardiac arrest, cardiac disorder, and disease progression). No deaths occurred in the KRd 56 mg/m^2 group (Biran et al. 2018). The median weekly dose of carfilzomib was 53.2 mg/m^2 for subjects administered 20/56 mg/m^2 and 62.4 mg/m^2 for subjects administered 20/70 mg/m^2. The median relative dose intensity of carfilzomib was 90.7 for subjects administered 20/56 mg/m^2 and 88.2 for subjects administered 20/70 mg/m^2. The median weekly dose and the relative dose intensity suggest that 20/56 mg/m^2 weekly dose was tolerable.

Available efficacy results indicated similar efficacy (as determined by ORR) with either KRd 56 mg/m^2 or KRd 70 mg/m^2 (90.0% versus 89.1%, respectively) to the effect previously reported for twice-weekly KRd (27 mg/m^2) in the randomized phase 3 ASPIRE study (Biran et al, 2018).

Based on evidence from phase 2 studies of KPd, weekly doses up to 70 mg/m² in subjects with first relapse and up to 54 mg/m² in subjects with advanced myeloma using a twice-weekly schedule of carfilzomib have been tolerated (Sonneveld et al, 2018;

Protocol Number: 20170596

**Date:** 20 May 2019 **Page 43 of 132** 

Shah et al, 2015). Consistent with the observation from the A.R.R.O.W. study, that adjustment from a twice-weekly to a once-weekly schedule was demonstrated to have a favorable benefit/risk profile with no new safety issues identified, the CFZ013 trial identified 56 to 70 mg/m² weekly carfilzomib combined with Rd to have an acceptable safety profile. Given these data, this phase 2 study will evaluate the 56 mg/m² once-weekly dose schedule for KRd and KPd triplet therapies.

## 5.5 Patient Input on Study Design

Not applicable.

# 6. Study Population

Investigators will be expected to maintain a screening log of all potential study candidates that includes limited information about the potential candidate (eg, date of screening). This log may be completed and updated via the Interactive Voice/Web Response System (IXRS).

Eligibility criteria will be evaluated during screening.

Before any study-specific activities/procedures, the appropriate written informed consent must be obtained (see Section 12.3).

Prospective approval of protocol deviations to recruitment and enrollment criteria, also known as protocol waivers or exemptions, will not be provided.

#### 6.1 Inclusion Criteria

Subjects are eligible to be included in the study only if all of the following criteria apply:

- Subject has provided informed consent prior to initiation of any study specific activities/procedures.
- 102 Males or females ≥ 18 years of age.
- 103 Relapsed MM after last treatment or refractory while receiving non-proteasome inhibitor therapy.
- 104 Measurable disease with at least 1 of the following assessed within 21 days prior to enrollment:
  - immunoglobulin G (IgG)MM: serum monoclonal protein (M-protein) level
     ≥ 1.0 g/dL
  - IgA, IgD, IgE multiple myeloma: serum M-protein level ≥ 0.5 g/dL
  - urine M-protein ≥ 200 mg per 24 hours
  - in subjects without measurable serum or urine M-protein, serum free light chain (SFLC) ≥ 100 mg/L (involved light chain) and an abnormal serum kappa lambda ratio.
- Eastern Cooperative Oncology Group Performance Status (ECOG PS) of 0 to 1 (Section 12.10)

Protocol Number: 20170596

**Date:** 20 May 2019 Page 44 of 132

Subjects must have at least partial response (PR) to at least 1 line of prior therapy.

- Subjects must have received at least 1 but not more than 3 prior lines of therapy for MM (induction therapy followed by stem cell transplant and consolidation/maintenance therapy will be considered as 1 line of therapy; see Section 12.11).
- 109 Measured creatinine clearance (radionucleotide or 24-hour urine) or calculated creatinine clearance per the Chronic Kidney Disease Epidemiology Collaboration formula, of ≥ 30mL/min/1.73 m² within 21 days of enrollment (see Section 12.13).

#### Kd Arm

Prior therapy with a PI is allowed as long as the subject was not removed due to toxicity (except for neuropathy, see criterion 213), and if received carfilzomib must have achieved at least a PR and have at least a 6-month carfilzomib treatment-free interval from last dose received until enrollment.

#### KRd Arm

Prior therapy with a PI or lenalidomide is allowed as long as the subject had at least a PR to most recent therapy with PI or lenalidomide, was not removed due to toxicity (except for neuropathy, see criterion 213), and if received carfilzomib must have at least a 6-month carfilzomib treatment-free interval from last dose received until enrollment.

#### KPd Arm

Prior therapy with a PI is allowed as long as the subject had at least a PR to most recent therapy with PI, was not removed due to toxicity (except for neuropathy, see criterion 213), and if received carfilzomib must have at least a 6-month carfilzomib treatment-free interval from last dose received until enrollment.

#### 6.2 Exclusion Criteria

Subjects are excluded from the study if any of the following criteria apply:

## Disease-related

- 201 Waldenström macroglobulinemia.
- 202 Multiple myeloma of IgM subtype.
- 203 POEMS syndrome (polyneuropathy, organomegaly, endocrinopathy, monoclonal protein, and skin changes).
- 204 History of plasma cell leukemia.
- Subjects with nephrotic range proteinuria (≥ 3 g albumin for 24 hours urine OR ≥ 2 g albumin/1 g of creatinine on a random urine specimen).
- 207 Myelodysplastic syndrome.
- 248 Primary amyloidosis (patients with multiple myeloma with asymptomatic deposition of amyloid plaques found on biopsy would be eligible if all other criteria are met).

Protocol Number: 20170596

**Date:** 20 May 2019 **Page 45 of 132** 

## **Other Medical Conditions**

208 History of other malignancy within the past 3 years, with the following exceptions:

- Malignancy treated with curative intent and with no known active disease present for ≥ 3 years before enrollment and felt to be at low risk for recurrence by the treating physician
- Adequately treated non-melanoma skin cancer or lentigo maligna without evidence of disease
- Adequately treated cervical carcinoma in situ without evidence of disease
- Adequately treated breast ductal carcinoma in situ without evidence of disease
- Prostatic intraepithelial neoplasia without evidence of prostate cancer
- Adequately treated urothelial papillary noninvasive carcinoma or carcinoma in situ
- Treated medullary or papillary thyroid cancer
- Similar neoplastic conditions with an expectation of > 95% five-year disease-free survival
- Known HIV infection, hepatitis C infection (subjects with hepatitis C that achieve a sustained virologic response following antiviral therapy are allowed), or hepatitis B infection (subjects with hepatitis B surface antigen or core antibody that achieve sustained virologic response with antiviral therapy directed at hepatitis B are allowed).
- 210 Active acute or chronic graft-versus-host disease (any grade).
- Acute active infection requiring systemic antibiotics, antifungal, antiviral (except antiviral therapy directed at hepatitis B) agents within 14 days prior to enrollment.
- 212 Known cirrhosis.
- 213 Significant neuropathy (grades 3 to 4, or grade 2 with pain) within 14 days prior to enrollment.
- Subjects with pleural effusions requiring thoracentesis or ascites requiring paracentesis within 14 days prior to enrollment.

# **Cardiopulmonary Conditions**

- Uncontrolled hypertension, defined as an average systolic blood pressure ≥ 160 mmHg or diastolic ≥ 100 mmHg (see Section 12.12 for more details). Subjects with controlled hypertension are eligible.
- Active congestive heart failure with or without reduced ejection fraction (NYHA Class III to IV), symptomatic ischemia, uncontrolled arrhythmias, clinically significant electrocardiogram (ECG) abnormalities, screening ECG with corrected QT interval (QTc) of > 470 msec, pericardial disease, myocardial infarction within 4 months prior to enrollment.
- 217 Known chronic obstructive pulmonary disease.
- 218 Known interstitial pneumonitis.

Protocol Number: 20170596

**Date:** 20 May 2019 **Page 46 of 132** 

# **Prior/Concomitant Therapy**

- 219 Immunotherapy within 21 days prior to enrollment.
- 220 Chemotherapy with approved anticancer therapeutic within 21 days prior to enrollment.
- 221 Glucocorticoid therapy (prednisone > 30 mg/day or equivalent) within 14 days prior to enrollment.
- Focal radiation therapy within 7 days prior to enrollment. Radiation therapy to an extended field involving a significant volume of bone marrow within 21 days prior to enrollment (ie, prior radiation must have been to less than 30% of the bone marrow).
- 223 Major surgery (except kyphoplasty) within 28 days prior to enrollment.
- 224 Autologous or allogeneic stem cell transplant within 90 days prior to enrollment.
- 225 Contraindication to dexamethasone, lenalidomide, or pomalidomide.
- 226 Known history of allergy to Captisol (a cyclodextrin derivative used to solubilize carfilzomib).
- 227 Intolerance to intravenous (IV) hydration.

# **Prior/Concurrent Clinical Study Experience**

Currently receiving treatment in another investigational device or drug study, or less than 30 days since ending treatment on another investigational device or drug study(ies). Other investigational procedures while participating in this study are excluded.

## **Organ Function Assessments**

- Hepatic dysfunction within 21 days prior to enrollment (see Section 7.1.1.2.1):
  - bilirubin ≥ 1.5 times the upper limit of normal (ULN)
  - aspartate aminotransferase (AST) or alanine aminotransferase (ALT)
     ≥ 3 times the ULN
- 230 Left ventricular ejection fraction < 40% assessed by transthoracic echocardiogram.
- 231 Severe valvular disease assessed by transthoracic echocardiogram.
- 232 Severe right-ventricular dysfunction assessed by transthoracic echocardiogram.
- 233 Right-ventricular systolic pressure > 40 mm Hg assessed by transthoracic echocardiogram.
- Absolute neutrophil count (ANC) < 1 x  $10^9$ /L within 21 days prior to enrollment. Screening ANC should be independent of growth factor support for  $\geq$  1 week.

Protocol Number: 20170596

**Date:** 20 May 2019 Page 47 of 132

Hemoglobin < 80 g/L within 21 days prior to enrollment. Use of erythropoietic stimulating factors and red blood cell (RBC) transfusions per institutional guidelines is allowed, however most recent RBC transfusion may not have been done within 7 days prior to obtaining screening hemoglobin.

Platelet count <  $50 \times 10^9$ /L ( $\leq 30 \times 10^9$ /L if myeloma involvement in the bone marrow is > 50%) within 21 days prior to enrollment. Subjects should not have received platelet transfusions for at least 1 week prior to obtaining the screening platelet count.

# **Other Exclusions**

- Male subjects with a female partner of childbearing potential who are unwilling to practice sexual abstinence (refrain from heterosexual intercourse) or use a condom with spermicide during treatment and for an additional 90 days after the last dose of study drug(s). Refer to Section 12.5 for additional contraceptive information.
- Male subjects with a pregnant partner who are unwilling to practice abstinence or use a condom during treatment and for an additional 90 days after the last dose of study drug(s).
- Male subjects unwilling to abstain from donating sperm during treatment and for an additional 90 days after the last dose of study drug(s).
- Subject has known hypersensitivity to any of the products or components to be administered during dosing, including hypersensitivity to antiviral drugs.
- Subject likely to not be available to complete all protocol required study visits or procedures, and/or to comply with all required study procedures (eg, Clinical Outcome Assessments [COAs]) to the best of the subject and investigator's knowledge.
- 247 History or evidence of any other clinically significant disorder, condition or disease (with the exception of those outlined above) that, in the opinion of the investigator or Amgen physician, if consulted, would pose a risk to subject safety or interfere with the study evaluation, procedures or completion.

## Kd Arm

- Female subject is pregnant or breastfeeding or planning to become pregnant or breastfeed during treatment and for an additional 30 days after the last dose study drug(s).
- Female subjects of childbearing potential unwilling to use 1 highly effective method of contraception during treatment and for an additional 30 days after the last dose of study drug(s). Refer to Section 12.5 for additional contraceptive information.
- Female subjects of childbearing potential with a positive pregnancy test assessed at screening and/or ay 1 by a serum pregnancy test and/or urine pregnancy test.

Protocol Number: 20170596

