# 5.2 Number of Subjects

A total of approximately 75 subjects will be enrolled in the study with approximately 25 subjects in each arm.

Subjects in this clinical investigation shall be referred to as "subjects". A sample size of approximately 75 subjects will provide for descriptive statistics to be generated for patient safety and treatment adherence. For the sample size justification, see Section 10.1.

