**Date**: 20 May 2019 **Page 48 of 132** 

## **KRd and KPd Arms**

Female subjects of childbearing potential unwilling to use 2 methods of contraception (1 of which must be highly effective; see Section 12.5) during the study and for an additional 30 days after the last dose of study drug. Additionally, subjects must be using contraception at least 28 days prior to initiating treatment. Refer to Section 12.5 for additional contraceptive information.

253 Female subjects of childbearing potential with a positive serum pregnancy test assessed within 14 days prior to first dose of study drug or a positive urine pregnancy test within 24 hours prior to first dose. In addition, females of childbearing potential must agree to pregnancy testing weekly during the first 4 weeks of pomalidomide or lenalidomide use followed by a pregnancy test every 4 weeks in females with regular menses or every 2 weeks in females with irregular menstrual cycles.

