#### 9.2.3.1.5 Pregnancy and Lactation

Details of all pregnancies and/or lactation in female subjects and, if indicated, female partners of male subjects will be collected after the start of study treatment and until 30 days (for female subjects) and 90 days (for female partners of male subjects) after the last dose of study drug(s).

If a pregnancy is reported, the investigator is to inform Amgen within 24 hours of learning of the pregnancy and/or lactation and is to follow the procedures outlined in Section 12.5. Amgen Global Patient Safety will follow-up with the investigator regarding additional information that may be requested.

Abnormal pregnancy outcomes (eg, spontaneous abortion, fetal death, stillbirth, congenital anomalies, ectopic pregnancy) are considered serious adverse events.

Further details regarding pregnancy and lactation are provided in Section 12.5.

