#### Collection of Lactation Information

- Investigator will collect lactation information on any female subject who breastfeeds
  while taking protocol-required therapies through 30 days after the last dose of
  protocol-required therapies.
- Information will be recorded on the Lactation Notification Worksheet (see below) and submitted to Amgen Global Patient Safety within 24 hours of the investigator's knowledge of event.
- Study treatment will be discontinued if female subject breastfeeds during the study.
- With the female subjects signed authorization for release of mother and infant health information, the investigator will collect mother and infant health information and complete the lactation questionnaire on any female subject who breastfeeds while taking protocol-required therapies through 30 days after discontinuing protocol-required therapies.

Protocol Number: 20170596

Page 116 of 132 **Date:** 20 May 2019

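### Breastfeeding is an entry exclusion only in the Kd arm, yet Appendix 5 stops study treatment in every arm if a subject breastfeeds

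*Protocol*

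**What the plan says.** Section 6.2 of the protocol has exclusion criteria common to all arms, then one list for the Kd arm and another for the KRd and KPd arms.

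- **Kd Arm.** One of three items excludes a woman if "Female subject is pregnant or breastfeeding or planning to become pregnant or breastfeed during treatment" or in the 30 days after the last dose. The other two concern contraception and a positive pregnancy test.
- **KRd and KPd Arms.** There are two items. The first begins "Female subjects of childbearing potential unwilling to use 2 methods of contraception". The second begins "Female subjects of childbearing potential with a positive serum pregnancy test assessed within 14 days prior to first dose of study drug" and goes on to require agreement to repeat pregnancy testing.
- **All arms.** The nearest general criterion is number 225, under Prior/Concomitant Therapy: "Contraindication to dexamethasone, lenalidomide, or pomalidomide".

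Two later parts of the protocol deal with lactation without separating the arms. Section 9.2.3.1.5 requires collection of "Details of all pregnancies and/or lactation in female subjects" up to 30 days after the last dose. Appendix 5 (Section 12.5), under Collection of Lactation Information, states: "Study treatment will be discontinued if female subject breastfeeds during the study".

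**The concern.** The protocol treats breastfeeding as incompatible with study treatment in every arm but asks about it at entry in only one. All three arms receive carfilzomib and dexamethasone, and KRd and KPd add lenalidomide or pomalidomide, so the arms with more drugs have the weaker entry screen. No reason is given. KRd and KPd were added by Amendment 3 to a protocol that had been Kd only, so a criterion left behind under the Kd heading is a plausible explanation, though that is inference.

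Two things are at stake. An infant may be exposed from the first dose until the site applies Appendix 5, if the mother has not weaned. The mother then has a treatment stop that screening could have avoided. A woman who weans before dosing is not affected. The gap is confined to lactation, because the KRd/KPd items on testing and contraception deal with pregnancy at entry and with planned pregnancy.

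**Working it through.** This is mainly a comparison of text in the current (Amendment 4) protocol.

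**Step 1: where breastfeeding is named as an exclusion.**

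| Part of Sections 6.1 and 6.2 | Items naming breastfeeding |
|---|---|
| Kd Arm exclusions | 1 of 3 |
| KRd and KPd Arms exclusions | 0 of 2 |
| Criteria common to all arms | none |
| Arm-specific inclusion criteria | none |

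**Step 2: whether another criterion reaches it.** A breastfeeding woman can have a negative pregnancy test and agree to two contraceptive methods, so both KRd/KPd items can be met. Criterion 225 does not name lactation, and the protocol does not say that lactation is a contraindication to these drugs. Criterion 225 applies to Kd subjects too, yet an express breastfeeding exclusion was still written for that arm. Criterion 247 concerns clinically significant disorders or conditions and depends on the opinion of the investigator or sponsor physician.

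**Step 3: order of events.** Under Section 6.3 a subject is enrolled once the investigator decides that all eligibility criteria are met. Section 6.2 is therefore what the site checks before dosing. The Appendix 5 rule takes effect when a subject breastfeeds on study.

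**Step 4: size.** Inputs are "A total of approximately 75 subjects will be enrolled in the study with approximately 25 subjects in each arm" (Section 5.2), the median age at diagnosis of 70 (Section 3.2.1), and the planned 95% CI half-width of 18.1 points at 75% completion with 25 subjects (Section 10.1, taken as stated).

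- Subjects entering under the KRd/KPd list: 2 × 25 = 50, and 50/75 = 67% of the planned total.
- Number affected: not given in the documents; assumed to be 0 or 1.
- Effect of one forced stop on an arm's 12-cycle completion proportion: 1/25 = 4.0 percentage points. She would stay in the denominator, because the safety set keeps everyone who received a dose, and Section 5.2.1 allows no replacement.
- With no such subject, the effect is 0 points.

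**The case against.** The strongest reply is that the protocol never permits breastfeeding on treatment. An entry criterion and an on-study stopping rule are different instruments, and a site that knows Appendix 5 has no basis for dosing a breastfeeding woman. Three general criteria might also screen her out: number 225, number 247, and the exclusion of subjects unlikely to comply with study requirements. The lenalidomide and pomalidomide REMS programs are mandatory in their arms, and they, the consent form and the product manual may address lactation. Finally, the count of 50 includes men and postmenopausal women, and lactation is very unlikely in relapsed or refractory myeloma after one to three prior lines.

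Much of this stands as a limit on size. The 50 is the number governed by the list, not the number at risk, and zero affected subjects is quite possible. It is also true that sites are not given contradictory instructions. What is missing is an explicit screening line.

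The gap itself remains. The three general criteria are indirect, and number 247 is discretionary. The protocol's REMS sections mention pregnancy monitoring but state no lactation rule, and what the external documents say cannot be checked here. Relying on Appendix 5 leaves the safeguard to the site's recall of an appendix when an explicit entry check was thought necessary for Kd.

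**Conclusion.** The point holds. For KRd and KPd, the written entry criteria can admit a woman whom Appendix 5 would then require to stop treatment, while the Kd criteria exclude her at screening.

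It is minor. No estimate, analysis or sample-size statement is threatened: even one affected subject would move one arm's completion proportion by 4 points, against a planned half-width of 18.1. The reason to act is infant safety and agreement between the eligibility and stopping rules. This rests on two assumptions: that 0 or 1 subject would be affected, and that infant exposure through breastfeeding is unwanted. The documents give no data on transfer of the drugs into milk; the second assumption is read from the protocol's own stopping rule and from the Kd exclusion.

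**What to change.** Move the existing Kd criterion on pregnancy and breastfeeding, including planned pregnancy or breastfeeding and the 30-day period after the last dose, to Other Exclusions in Section 6.2 so that it covers all three arms. Repeating it under KRd and KPd Arms would do equally well. Either way, entry would then agree with Appendix 5 and Section 9.2.3.1.5 in every arm.

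The cost is one existing sentence moved or repeated. No visit, test or procedure is added, and no analysis changes.
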